For hypotheses 3A and 3B, the following preprocessing and analytical parameters will be used. Preprocessing: Post-acquisition preprocessing and statistical analysis of imaging data will be performed using FEAT (FMRI Expert Analysis Tool) Version 5.98, part of FSL (FMRIB's Software Library). Data will be preprocessed using scripting tools from FEAT. Non-brain signal will be removed using FSL's BET brain extraction. Scans will be corrected for motion using FSL's linear registration and scans will be spatially smoothed using a Gaussian kernel of 8 mm FWHM. Participants with head motion ≥ 0.2 mm will be excluded from the analyses¹²⁷. Motion artifacts will be identified and scrubbed from each subject's data. Scans will be spatially co-registered with a standardized anatomical template (Montreal Neurological Institute) using a 12 parameter affine transformation. Analysis: Functional connectivity will be measured using a psychophysiologic interaction seed-based approach¹²⁹⁻¹³⁰. PPI analysis is used to assess the functional coupling between different brain regions. The PPI is defined as the change in connectivity of one area (i.e., the seed region) to another in relation to the experimental context (e.g., alcohol vs. neutral cues). PPI analyses for resting state, trauma and alcohol cues will be performed separately. Customized sq. wave forms representing the trauma run (1=trauma block and -1=neutral block) and the alcohol cue run (1=alcohol block and -1=neutral block) the duration of each block will be convolved with a double-gamma hemodynamic response function. A mask of the seed region will be made using a 12-mm diameter sphere located in the center of the AMY using the MNI coordinates (x, y, z = ± 22 , 0, -22). The transformation parameters described above will also be applied to the mask. For each subject, the mean corrected and high pass filtered time series of the BOLD signal in the AMY will be extracted and used in a single subject whole brain PPI analysis. The PPI model will include the task vector, time series of the BOLD signal in the AMY, a term representing the positive task x seed interaction, and a term representing the negative task x seed interaction. The first level analysis will generate contrast images of the parameter estimates for each of the four regressors. Voxels will be thresholded at $Z > 2.3$ using a corrected cluster threshold of $p = 0.05$. The contrast images of the parameter estimates of the positive and negative task x seed interactions will be combined for group-level t-tests to identify regions that exhibited altered connectivity with the AMY during the trauma and alcohol cues as compared to neutral cues. All group-level results will be thresholded at $Z > 2.3$ using a corrected cluster threshold of $p = 0.05$. Separate linear regression tests will be used to test for associations between PFC-AMY connectivity at baseline and improvement in AUD and PTSD symptoms during treatment. Changes in total standard drinks will be regressed against the parameter estimate obtained from the center voxel from each cluster that exhibited a significant task x seed interaction with the AMY at rest and in response to the alcohol cues (Hypothesis 3A). Changes in CAPS-5 total scores will be regressed against the parameter estimate obtained from the center voxel from each cluster that exhibited a significant task x seed interaction with the AMY at rest and in response to the trauma cue (Hypothesis 3B). Further exploratory analyses will examine change in PFC-AMY connectivity from pre- to post-treatment and associations with alcohol and PTSD outcomes, both within and between medication groups.

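### No physiological or white-matter/CSF nuisance regressors are specified for the connectivity models, which mainly weakens the resting-state predictor in Hypotheses 3A and 3B

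*Combined protocol and SAP*

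**What the plan says.** All of this is in Statistical Analyses, under Hypotheses 3A and 3B.

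- **First-level model.** "The PPI model will include the task vector, time series of the BOLD signal in the AMY", followed by "a term representing the positive task x seed interaction" and "a term representing the negative task x seed interaction". The text then confirms the count: "The first level analysis will generate contrast images of the parameter estimates for each of the four regressors".
- **Motion.** Three steps are planned outside that model: "Scans will be corrected for motion using FSL's linear registration", "Participants with head motion ≥ 0.2 mm will be excluded from the analyses" and "Motion artifacts will be identified and scrubbed from each subject's data". The motion metric behind the 0.2 mm limit and the scrubbing method are not given.
- **Seed signal.** "the mean corrected and high pass filtered time series of the BOLD signal in the AMY will be extracted". No other cleaning of the seed is described.
- **Rest.** The same interaction approach is named for the resting run, to be analysed separately from the cue runs. No model without task terms is written out for it.
- **Second level.** Change in total standard drinks (3A) and in CAPS-5 (3B) is regressed on the first-level estimate at the centre voxel of each significant cluster. No motion or noise covariate is named.

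**The concern.** The prognostic regressions use differences between people in amygdala-prefrontal coupling. Any signal that reaches both regions from a common non-neural source, such as heartbeat, breathing or CSF pulsation, adds to the seed-target coefficient in proportion to how noisy that person's scan is. The predictor then partly ranks people by noise.

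The planned steps leave this component in place. Realignment, exclusion and scrubbing act on head movement. The high-pass filter cannot be relied on for cardiac signal: at a TR of 2 s the highest resolvable frequency is 1/(2 × 2 s) = 0.25 Hz, so a heartbeat near 1 Hz (assumed) is aliased and can appear at frequencies that the filter passes.

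At stake is the power of the resting halves of 3A and 3B. If noise level also tracks clinical change, their error rate is at stake too.

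**Working it through.** **1. Count of terms.** Task, amygdala series, positive interaction, negative interaction: 4. This agrees with the plan's own count. None is a motion-parameter, white-matter, CSF, cardiac or respiratory term.

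**2. What the list can describe.** The resting run is six minutes of fixation without blocks (Neuroimaging Component). Three of the four listed terms need a task vector, so the list cannot literally be the resting model. What remains is the amygdala series alone, and its coefficient is plain coupling.

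**3. Inputs.**
- Volumes per run: 360 s / 2 s = 180, taking the stated EPI repetition time for all runs.
- Sample: 140 imaging participants (Power and Sample Size) × 0.75 = 105. Applying the trial's 25% attrition to this subset is an assumption.
- True correlation: the plan gives d = 0.8 for its first imaging example. r = d/√(d² + 4) = 0.8/√4.64 = 0.37.
- Shared noise of 10, 20 or 30% of signal variance, and a nuisance estimate correlated 0.9 with the true nuisance. Both are assumed, because the documents give no noise data.

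**4. Resting predictor, power (simulation, 500 studies per setting).**

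| Shared noise | Without nuisance terms | With nuisance terms |
|---|---|---|
| 10% | 92% | 94% |
| 20% | 81% | 93% |
| 30% | 61% | 88% |

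Two further simulations that build the noise somewhat differently gave 95/88/70% and 86/75/59% without, against 96/95/91% and 94/92/88% with. Across all three, the loss is 1 to 8 points at 10% noise and 21 to 29 points at 30%.

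**5. Check by formula.** Power ≈ Φ(atanh(r_obs) × √(n − 3) − 1.96), with √102 = 10.10. In a separate simulation with shared noise SD at half the neural SD (0.25/1.25 = 20% of seed variance), the estimated seed coefficient correlated 0.74 with the true one without a nuisance term and 0.89 with a perfectly measured one.
- Without: r_obs = 0.37 × 0.74 = 0.274; atanh × 10.10 = 2.84; Φ(0.88) = 81%.
- With: r_obs = 0.37 × 0.89 = 0.329; atanh × 10.10 = 3.45; Φ(1.49) = 93%.

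Both agree with the 20% row.

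**6. Resting predictor, false positives.** With no true association and an assumed correlation of 0.3 between noise level and outcome, the rate at 10/20/30% noise was 15/29/55% without nuisance terms and 8/7/17% with them. A second simulation gave 9/23/45% and 5/6/16%. With noise unrelated to outcome, the rate was about 4-5% either way.

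**7. Cue interaction terms.** These used a simplified model with one interaction term.
- With noise constant across blocks and the same 0.3 noise-outcome correlation, the false-positive rate was 4/5/6% at 10/20/30% noise, which is near nominal. The seed term in the same runs gave 8/33/54%.
- With noise 50% larger in cue blocks (assumed), the rate was about 11% without a nuisance term and 3% with one.
- The correlation of the estimated interaction with the true one fell from 0.89 without shared noise to 0.85 (constant noise) or 0.82 (larger in cue blocks).

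**The case against.** **The list may cover only terms of interest.** This is possible. However, the task vector and the seed series are listed although neither is the interaction effect, which reads like a full model. On the generous reading nuisance terms are still unspecified, and the same edit resolves it.

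**Motion is already handled.** This stands in large part. A 0.2 mm limit is not merely a screen for gross movement, and scrubbing may itself be carried out with per-volume confound regressors. A reader might infer from the four-term list that the plan ignores motion; the documents do not support that. None of the three steps addresses physiological or white-matter/CSF signal.

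**The cue predictors are contrasts.** This stands. Noise common to cue and neutral blocks largely cancels. A reader might carry the resting figures over to all of 3A and 3B, but step 7 shows that this would be wrong. Trauma scripts could change breathing or movement between blocks, but the documents give no data on it.

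**The effect size could be larger.** The plan's relapse comparison has d = 1.0, so r = 1/√5 = 0.45. Carrying the same attenuation over gives power of about 98/93/78% without nuisance terms. The loss is then small except at 30% noise. At 10% noise the two-point difference at r = 0.37 (92 against 94%) is also close to simulation error, since √(0.92 × 0.08/500) is 1.2 points for one of the two rates.

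**False associations are conditional.** This stands. They need noise level to be related to drinking or CAPS-5 change, and 0.3 is an assumed value. A reader might infer that the plan produces spurious predictors; nothing in the documents shows that it would.

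**Conclusion.** The point holds in a limited form. As written, the plan has no step that removes physiological or white-matter/CSF signal shared by seed and target, and it has no usable model for the resting run. For the resting predictor, the expected cost at n = 105 and r = 0.37 runs from about 2 points of power (10% shared noise) to about 27 points (30%: 61 against 88%), and less if the true correlation is larger. This rests on assumed noise levels and an assumed quality of the nuisance estimate. The power loss needs only noise that varies between people. Inflated false positives also need noise that tracks outcome.

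For the alcohol and trauma interaction terms the effect is small unless noise differs between blocks. The primary clinical outcomes (drinking, CAPS-5, PCL-5) are untouched; only the imaging predictors of Aim 3 are affected.

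**What to change.** 1. State the resting model explicitly as a seed regression: amygdala series plus confounds, without task or interaction terms.
2. Add the six realignment parameters and the mean white-matter and mean CSF signals as confound regressors to every first-level model (rest, alcohol, trauma). Keep the planned scrubbing.
3. In the same edit, say how scrubbing is done and which motion metric the 0.2 mm limit refers to.

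The cost is 6 + 2 = 8 of 180 degrees of freedom per run (4.4%) before scrubbing, and some set-up work. The grey-matter, white-matter and CSF segmentation of the T1 images is already planned under Exploratory Hypothesis 4, so no new data are needed. A little sensitivity is lost in the cue runs if motion tracks the blocks.

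The change does not remove the problem entirely. At 30% noise related to outcome, the simulated false-positive rate was still 17% (55% without the terms). A sensitivity analysis with each person's mean motion as a second-level covariate would be a cheap addition, though it covers only the motion part.

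### The group-level cluster error rate of 5% at Z > 2.3 rests on an unstated and unchecked noise-shape assumption and on an unstated sidedness; a two-sided sign-flip permutation null would remove both dependencies

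*Combined protocol and SAP*

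**What the plan says.** The relevant text is in the combined protocol and SAP, Statistical Analyses, in the analysis paragraph that follows Hypotheses 3A and 3B.

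- **Software:** preprocessing and statistical analysis use "FEAT (FMRI Expert Analysis Tool) Version 5.98, part of FSL (FMRIB's Software Library".
- **Smoothing:** "scans will be spatially smoothed using a Gaussian kernel of 8 mm FWHM".
- **Search region:** the amygdala time series is "used in a single subject whole brain PPI analysis". No prefrontal mask is named.
- **Group test:** the positive and negative interaction images are "combined for group-level t-tests to identify regions that exhibited altered connectivity with the AMY" under cue compared with neutral blocks.
- **Error control:** "All group-level results will be thresholded at $Z > 2.3$ using a corrected cluster threshold of $p = 0.05". The first-level maps have the same rule.
- **Use of the result:** the centre-voxel estimate of every significant cluster is then related by linear regression to change in standard drinks (3A) or in CAPS-5 (3B).

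Rest, trauma and alcohol maps are analysed separately. The text does not say whether the corrected p-value comes from a random-field formula or from permutation, whether the t-tests are one-sided or two-sided, or which group-level variance model applies. It gives no check of the spatial assumptions.

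**The concern.** A Z cut-off paired with a corrected cluster p-value in FEAT is most naturally read as a random-field cluster-extent test. That test does not build its null distribution from the participants. It asks how large a cluster above Z = 2.3 would be in a Gaussian field whose smoothness is local and Gaussian in shape. What is tested is therefore joint: no cue effect, and noise of that shape. If the correlation of the noise has a long-range tail, large clusters can form above a threshold as low as 2.3 (one-sided voxel p = 0.0107) with no cue effect at all.

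The maps are estimates of seed coupling, and the plan describes the method in these words: "PPI analysis is used to assess the functional coupling between different brain regions". It offers no reason to expect the correlation in the noise to stop at the 8 mm kernel. Other parts of the Statistical Analyses section do check assumptions: over-dispersion and excess zeros for drinks, residual normality and constant variance for CAPS-5. The imaging test has no counterpart.

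Direction matters too. The aim is to find altered connectivity, which can mean more or less. If the 5% applies to each one-sided map, the rate for the two-direction search is higher.

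At stake is the set of regions reported under Aim 3, and the set of clusters that become predictors in 3A and 3B.

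**Working it through.** **Inputs from the plan.** Z > 2.3; corrected cluster p = 0.05; 8 mm smoothing; whole-brain search; separate rest, trauma and alcohol maps.

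**Assumptions, not in the documents.** An ellipsoidal search volume of 1.53 or 1.66 litres; a null field standing for the group Z-map; and the shape of the spatial correlation, (1 − w) × Gaussian (8 mm kernel) + w × exp(−distance/c), where w is the tail share and c its length.

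**Step 1: the plan's own figure.** The plan gives no cluster extent, residual smoothness or voxel count, so its 0.05 cannot be reproduced exactly. What can be done is to compute the extent cut-off that the random-field formula would set. For V = 207,319 voxels of 2 mm (1.66 L) and FWHM of 8 mm (4 voxels):

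- Smoothness term: (4 ln 2)^1.5 / 4³ = 0.0721.
- Expected clusters: E[m] = V × 0.0721 × (2π)^−2 × (2.3² − 1) × exp(−2.3²/2) = 115.4.
- Expected voxels above threshold: 207,319 × 0.010724 = 2,223.
- β = (Γ(2.5) × 115.4 / 2,223)^(2/3) = 0.168.
- Setting 1 − exp(−E[m] × exp(−β k^(2/3))) = 0.05 gives exp(−β k^(2/3)) = 0.0513/115.4 = 0.000445, so k = (7.72/0.168)^1.5, about 311 voxels (2.5 mL).

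**Step 2: error rate under no effect.** The cut-off was recomputed for each scenario from the smoothness estimated between neighbouring voxels. Null fields were then simulated, and those with any cluster at or above the cut-off were counted. Rates are per one-sided map.

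| Assumed tail share w | 1.53 L, c = 12 mm, 800 fields | 1.53 L, c = 12 mm, 150 fields | 1.66 L, c = 10 mm, 600 fields |
|---|---|---|---|
| 0% | 1.7% | about 1% | 2.3% |
| 5% | 6% | about 6% | not run |
| 10% | 11% | about 11% | not run |
| 15% | 18% | not run | not run |
| 20% | 23% | about 26% | 26% |

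Monte Carlo standard errors, √(p(1 − p)/n): for 800 fields, 0.5 points at 1.7%, 0.8 at 6%, 1.1 at 11% and 1.5 at 23%. For 600 fields, 0.6 points at 2.3% and 1.8 at 26%. The 6% at a 5% tail is therefore not distinguishable from 5%. Linear interpolation in the 800-field column puts the crossing at 5 × (5 − 1.7)/(6 − 1.7) = 3.8%, so about 4-5%. Heavier assumed tails (w of 40-50%, c of 10-14 mm, 600 fields) gave 61-73%.

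**Step 3: both directions.** With a true 5% per direction, 1 − 0.95² = 9.75% per map. At a 10% tail, 1 − (1 − 0.111)² = 21%. The simulated either-direction rates were 3.3%, 12%, 20%, 33% and 41% at tails of 0, 5, 10, 15 and 20% (800 fields), and about 3%, 11%, 22% and 47% at 0, 5, 10 and 20% (150 fields). With no tail, even the two-direction rate stays below 5%.

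**Step 4: sign-flip null.** A small check (30 maps, 0.36 L, 59 flips, 200 datasets, largest cluster over both directions) gave 2.0% at w = 0 and 5.5% at w = 20%. At a true 5%, the standard error with 200 datasets is 1.5 points, so both lie within about two standard errors of 5%. No parametric rate was computed at this smaller volume, so this is not a like-for-like comparison with Step 2. The case for the method rests on its construction: under sign symmetry the error is held at 0.05 whatever the spatial shape of the noise.

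**Step 5: a higher threshold alone.** With the parametric null at Z > 3.1, the one-sided rate was 1.7-3.0% under Gaussian-shaped correlation. It was 3.8% (w = 10%, c = 15 mm) and 10% (w = 20%, c = 12 mm) with 250 fields each, and 10-31% across tails of 20-50% with 600 fields each.

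**The case against.** The strongest reply is that the plan never says the null is parametric. It names FEAT and a corrected threshold, and permutation is also available in FSL. Moreover, when the random-field assumptions hold, the test is conservative, at about 1-2% per one-sided map. All of the inflation comes from a tail whose weight and length the documents do not give, and coupling between regions within a person does not prove a long-range tail in the noise between people. This stands as far as size is concerned. A reader might infer that clusters will be declared at several times 5%; the documents do not support that. They support only that the 5% is conditional on something unstated and unchecked.

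A second reply concerns consequences. A reader might infer that false clusters inflate the 3A and 3B tests. They do not do so directly: clusters are selected on the cue-by-seed effect, not on drinks or CAPS-5. A false cluster adds a noise predictor and one more regression, but leaves the error of any single regression at its own level. 3A and 3B also concern prefrontal-amygdala connectivity, so a whole-volume rate overstates the chance of a false cluster within that region, although no prefrontal mask is named. This stands too.

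A third reply is that a figure for several maps together would mix two issues. For four one-sided maps treated as independent, a 10% tail gives 1 − (1 − 0.111)^4 = 37.5%, but a fully valid 5% per map already gives 1 − 0.95^4 = 18.5%. About half is ordinary multiplicity, so the per-map rates are the relevant ones here.

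None of this answers the core: the plan states 5% without saying what secures it, and a method that does not need the noise-shape assumption is readily available.

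**Conclusion.** The point holds in conditional form. On the natural reading, the group-level 5% depends on local, Gaussian-shaped noise smoothness. Under the simulation assumptions, the rate per one-sided map runs from about 1-2% with no tail, through 5% at a tail of about 4-5%, to about 11% at a 10% tail and 23-26% at a 20% tail. A search in both directions roughly doubles these rates. Possible inflation is demonstrated; actual inflation in this trial is not, because the tail weight, the search volume and the group variance model are not in the documents.

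The scope is Aim 3 only: which regions are reported as altered, and how many noise predictors reach the 3A and 3B regressions. No NAC efficacy test on drinking, craving or PTSD severity is affected. This is a change the sponsor should make, held with medium confidence. It goes beyond a request for missing detail, because there is a specific and cheap method that secures the stated error rate under a weaker assumption.

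**What to change.** Keep the first-level and group-level models and the cluster-extent statistic. In the imaging analysis paragraph, state that the group-level corrected p-value will come from sign-flip permutation of the participants' contrast images, with the null distribution of the largest cluster taken over both directions, so that p = 0.05 is two-sided for each map. State the group variance model in the same place. If the sponsor prefers the parametric null, the plan should name it, state its sidedness, and justify the smoothness assumption at Z > 2.3. Raising the threshold to Z > 3.1 is not a remedy, since it only partly reduces the inflation under long-tailed noise.

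The cost is a sentence or two of text and extra computing time on data already planned for collection. The method relies on symmetry of the participants' contrast errors about zero. If the noise is long-tailed, some clusters that would have been declared will drop out.

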PROTOCOL TITLE: A Randomized Controlled Trial of N-Acetylcysteine for Alcohol Use Disorder and Comorbid PTSD

NCT02966873

November 9, 2019

PROTOCOL TITLE: A Randomized Controlled Trial of N-Acetylcysteine for Alcohol Use Disorder and Comorbid PTSD

The primary objective of the proposed Phase II study is to evaluate the effects of NAC in reducing (1) AUD severity and (2) PTSD symptomatology among individuals (N=200) with current AUD and PTSD. We will also use functional magnetic resonance imaging (fMRI) and proton magnetic resonance spectroscopy (MRS) to investigate the neural circuitry and neurochemistry underlying comorbid AUD/PTSD and prognostic indicators of positive treatment response. Secondary objectives are to evaluate the effects of NAC on impairment in associated areas of functioning (e.g., depression, anxiety, sleep, risky behaviors). In order to accomplish this we will (1) employ an intent-to-treat, double-blind, placebo-controlled randomized controlled trial that will consist of 12 weeks of treatment with NAC (2400 mg per day) or placebo medication; (2) examine standardized, repeated dependent measures of clinical outcomes at baseline, week 6, week 12, and 3-, 6-, and 12-month follow-up; and (3) employ advanced neuroimaging methodologies, a laboratory cue paradigm, and collect biologic measures of alcohol consumption. The following specific aims are proposed:

Specific Aim 1: To determine the efficacy of N-acetylcysteine (NAC), as compared to placebo, in reducing alcohol use severity.

Specific Aim 2: To determine the efficacy of N-acetylcysteine (NAC), as compared to placebo, in reducing PTSD symptomatology.

Specific Aim 3: To use multimodal neuroimaging techniques to investigate the pathophysiology underlying AUD and comorbid PTSD, and prognostic indicators of treatment outcome.

Human Subjects Involvement and Characteristics: A total of 200 adults between the ages of 18 and 70 will be recruited over a 5-year period. The inclusion/exclusion criteria are as follows:

Inclusion Criteria:

1. Male or female; any race or ethnicity; age 18 to 70 years old.
2. Subjects must be able to comprehend English.
3. Meet DSM-5 criteria for current alcohol use disorder (AUD).

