Neuroimaging Component. Given the severe negative outcomes associated with co-occurring AUD and PTSD and lack of effective treatments, investigation of the neural circuitry and neurochemistry underlying AUD/PTSD and involved in positive therapeutic response to NAC could be important in guiding future studies targeting this circuitry using other therapeutic agents or treatment modalities. To that end, fMRI and ¹H-MRS data will be acquired at baseline and end of treatment on all fMRI-eligible participants to examine (a) glutamate concentrations, (b) resting state connectivity, and (c) response to alcohol, trauma, and neutral cues. Scans will be conducted at the MUSC Center for Biomedical Imaging (see Facilities and Resources section), which houses a Siemens 3T TIM Trio MRI scanner (Siemens Medical, Germany). The neuroimaging component will involve three visits, each lasting 60-90 minutes. During visit 1 (baseline screening visit), we will develop the personalized imagery scripts for trauma and/or racial-based trauma, alcohol and neutral cues. During visit 2 (Randomization Visit, prior to medication initiation) and visit 3 (Post Treatment – 8 Visit), we will conduct the fMRI and ¹H-MRS scanning procedures. Women of childbearing age will receive a urine pregnancy test before each MRI. Imagery scripts will be developed according to standardized procedures⁴¹ and employed in our ongoing research (see Preliminary Studies section). The Wk 8 scan will be conducted approximately one hour post-NAC administration to ensure findings reflect effects of NAC¹²²⁻¹²³. Participants will be screened for metal using a handheld metal detector. Trained staff will position subjects on the scanner bed with foam padding placed around their head to prevent motion. Participants will wear headphones to listen to the audio-recorded scripts. During initial scanner tuning, localizing, and structural

Overview of neuroimaging session. Assessment of (a) ACC glutamate, (b) resting connectivity, and (c) response to alcohol, trauma and neutral cues.

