General. Baseline clinical and demographic characteristics will be collected and contrasts performed between treatment groups. Continuous and ordinal characteristics will be compared using a Wilcoxon Rank-Sum test statistic. Categorical characteristics will be compared using a Pearson Chi-Square test statistic. Baseline characteristics found to be significantly associated with primary outcome measures will be included as covariates in the analyses. All analyses will be performed on the intent-to-treat sample consisting of all randomized subjects. All analysis will be conducted using SAS v9.3 (SAS Institute, Cary, NC, USA).

Randomization. We will stratify by (1) AUD severity (TLFB) and (2) PTSD severity (CAP-5). Stratified random block randomization will be used to balance the randomization assignment with respect to these strata. The purpose of stratification is to distribute these potential prognostic factors equally across treatment groups.

Power and Sample Size. This study is powered to estimate the efficacy of NAC on the reduction in PTSD symptoms, alcohol use, and craving at the end of the treatment phase (final 3 weeks of treatment). This study builds on a recently completed pilot trial of NAC that assessed efficacy in reduction of PTSD symptomology and craving in a cohort of Veterans with PTSD and substance use disorders. In this promising pilot trial, we observed a clinically significant decrease in CAPS total scores following 8 weeks of treatment with NAC ($\Delta=26.8$) while the placebo response was attenuated ($\Delta=17.1$). Assuming a similar difference in treatment effects in a larger population, we will have 80% power with a type 1 error rate of 5% to detect this difference with 75 participants randomized to each of the two treatment arms (total

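### The Hypothesis 3A and 3B regressions have no medication term: adequate for a prognostic question, but unable to tell a general prognostic marker from a marker of response to NAC

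*Combined protocol and SAP*

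**What the plan says.** The analysis text for Hypotheses 3A and 3B first gives the general form: "Separate linear regression tests will be used to test for associations between PFC-AMY connectivity at baseline and improvement in AUD and PTSD symptoms". It then gives one regression per outcome. For 3A, "Changes in total standard drinks will be regressed against the parameter estimate obtained from the center voxel from each cluster" showing a significant task-by-seed interaction with the amygdala. For 3B, "Changes in CAPS-5 total scores will be regressed against the parameter estimate obtained from the center voxel from each cluster" of the same kind. No other regressor is named.

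Medication group does appear in the imaging analyses, but for other quantities. In the 3A/3B text, "Further exploratory analyses will examine change in PFC-AMY connectivity from pre- to post-treatment and associations with alcohol and PTSD outcomes", and these are to be done "both within and between medication groups". Under Exploratory Hypothesis 4, medication group is a factor in the glutamate mixed model, and associations of glutamate difference scores with outcome are also examined within and between groups. Neither analysis uses baseline connectivity as the predictor.

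The covariate rule under Statistical Analyses, General, admits baseline characteristics associated with the primary outcomes. Treatment assignment is not one of these.

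The purpose is worded in two ways. Specific Aim 3 and the two hypotheses are prognostic: they ask whether connectivity predicts outcome, and NAC is not named. The opening objectives paragraph likewise speaks of "the neural circuitry and neurochemistry underlying comorbid AUD/PTSD and prognostic indicators of positive treatment response". The Neuroimaging Component section gives two purposes: the circuitry and neurochemistry underlying AUD/PTSD, and those "involved in positive therapeutic response to NAC could be important in guiding future studies".

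**The concern.** All participants receive 12 weekly CBT sessions, and half also receive NAC. A regression of improvement on baseline connectivity that ignores arm therefore describes an average course under two regimens. A positive 3A or 3B result would show that connectivity goes with improvement. It would not show whether that holds equally in both arms, only on NAC, or only on placebo.

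This matters for how the result is used. If connectivity marks general prognosis, it describes who does well in CBT with either capsule. If it marks response to NAC, it bears on whom to treat and on which circuit a later agent should target, which is the use the Neuroimaging Component section has in view. The plan does not restrict the conclusion to the first reading, and no other planned analysis supplies the second for the baseline predictor.

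**Working it through.** **No figure in the plan to reproduce for this test.** The imaging power statements under Power and Sample Size concern two-group comparisons (PTSD against controls, relapsed against not relapsed) and a glutamate effect. None refers to a regression slope or an interaction.

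**1. What the slope without an arm term estimates.** Let the connectivity slope be b_N on NAC and b_P on placebo. Allocation is 1:1 (100 per arm), and connectivity is measured before randomised treatment, so it is unrelated to arm in expectation. Then

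slope ignoring arm ≈ (b_N + b_P)/2.

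Leaving arm out does not bias this average. Different pairs of slopes can share the same average, however. A simulation shows the consequence. Assumptions: N = 105, standardised connectivity, residual SD 1, a NAC main effect of 0.4 SD, 8,000 runs. The slopes are illustrative and are not taken from the plan.

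| True slopes NAC / placebo | Mean slope, no arm term | Significant | Mean interaction | Interaction significant |
|---|---|---|---|---|
| 0.3 / 0.3 (general prognosis) | 0.30 | 84% | 0.00 | 5% |
| 0.6 / 0 (NAC only) | 0.30 | 81% | 0.60 | 84% |
| 0 / 0.6 (placebo only) | 0.30 | 79% | −0.60 | 85% |
| 0.3 / −0.3 (opposite directions) | 0.00 | 5% | 0.60 | 84% |

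The planned test gives the same answer in the first three rows and sees nothing in the fourth. The interaction separates the general case from the others, and its sign separates NAC-only from placebo-only.

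**2. Treatment difference left in the residual (3B).** Inputs from Power and Sample Size: pilot CAPS changes of 26.8 on NAC and 17.1 on placebo, and 80% power at two-sided 5% with 75 per arm. The plan states no SD, so it has to be inferred.

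- Difference: 26.8 − 17.1 = 9.7.
- Standardised difference detectable at 75 per arm (two-sample t-test): 0.4605.
- Implied SD: 9.7/0.4605 = 21.1.
- With 1:1 allocation each arm mean lies 9.7/2 = 4.85 from the overall mean, so the share of variance due to arm is 4.85²/(21.1² + 4.85²) = 23.5/(445.2 + 23.5) = 0.050.

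Removing 5% of the variance multiplies the standard error of the slope by about √0.95 = 0.975. The gain in precision is small. The plan gives no figures for the corresponding share in 3A.

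**3. What an interaction could detect.** The plan expects 140 of 200 to be imaged, or 70 per arm. If its attrition of about 25% applies equally to this subset (an assumption), 140 × 0.75 = 105 remain, about 52 per arm. The detectable between-arm difference in Fisher z at 80% power, two-sided 5%, is 2.802 × √(2/(n − 3)):

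- n = 70: 2.802 × √(2/67) = 0.48.
- n = 52: 2.802 × √(2/49) = 0.57.

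If the placebo correlation were 0, these correspond to NAC correlations of about 0.45 and 0.51. The single slope ignoring arm needs only r of about 0.23 at N = 140 or 0.27 at N = 105.

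Interaction power at N = 105, for assumed correlations on NAC and placebo: 34% for 0.3 and 0; 20% for 0.4 and 0.2; 78% for 0.5 and 0. The head-motion exclusion would lower these figures further. The regressions are also repeated for each significant cluster, and the number of clusters is not known in advance.

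**The case against.** The strongest reply is that 3A and 3B do not ask about NAC. Aim 3 seeks prognostic indicators of outcome, and the hypotheses say that connectivity will predict reduction in drinking or CAPS-5. Hypotheses 1, 2 and 4, by contrast, each state a comparison with placebo. For a prognostic question, one slope across a randomised sample is a proper and unbiased estimate. This stands, and it rules out calling the planned test invalid.

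It can also be said that the plan never states that the arms are combined. That is true. It follows from the terms named and from the contrast with the neighbouring analyses, where medication group is mentioned. It is better described as an unspecified point than as a declared choice.

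A reader might also infer from the pilot that the slope mostly reflects something other than NAC. The plan reports a CAPS change of 26.8 on NAC "while the placebo response was attenuated" at 17.1, and 17.1/26.8 is 64%. The documents do not support that step. The ratio compares mean changes, and a mean change common to both arms goes into the intercept. It says nothing about how improvement varies with connectivity between people. The pilot was also an 8-week trial in Veterans with PTSD and substance use disorders, whereas this trial treats AUD with PTSD or subthreshold PTSD for 12 weeks.

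Lastly, the interaction has low power for moderate differences. That stands too. It is a reason to label the interaction exploratory, not a reason to leave the arms undistinguished.

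**Conclusion.** The point holds in a limited form. As written, the 3A and 3B regressions answer the prognostic question without bias, at a small cost in precision: about 5% of outcome variance for CAPS, resting on an SD of about 21 inferred from the power statement and on the pilot difference carrying over. They cannot support a statement about response to NAC, which is one of the two purposes given for the imaging. The arm-specific analyses of connectivity change and glutamate change do not fill that gap for the baseline predictor. This second conclusion follows from the model terms and does not depend on the illustrative slopes.

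A reader might go further and infer that 3A and 3B fail Aim 3, or that their slopes are biased. The wording of the aim and the randomisation contradict both. The efficacy analyses for Aims 1 and 2 are unaffected. This is a modest improvement to a non-primary aim.

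**What to change.** In the 3A and 3B regressions, include medication arm as a fixed term. State that the common connectivity slope is prognostic, describing course under CBT with either capsule, and that no claim about response to NAC will be drawn from it.

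Add an arm-by-baseline-connectivity interaction, labelled exploratory. Report the slope in each arm and the between-arm difference, each with a confidence interval. Limit any statement about response to NAC to that interaction. State in advance that a non-significant interaction is inconclusive, given the detectable differences shown above.

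The cost is two model terms on data already being collected, with no added participants, visits or scans. The drawback is the imprecision of the interaction.
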